7.4.7.2 Analyses of Other Safety Endpoints

Observations and changes from baseline in vital signs and laboratory tests including hematology, blood chemistry, and liver function measures will be summarized by treatment group for each scheduled visit, the maximum and minimum post-treatment values and the values at the End of Treatment visit.

Blood chemistry and hematology laboratory tests will be graded according to CTCAE (toxicity grade 1 to 5) Version 5.0, if applicable. The number and percentage of patients within each CTCAE grade will be summarized by throughout the whole study and by scheduled visit. The worst grade will be reported if a patient has multiple laboratory assessments during the interval analyzed.

For vital signs and ECG, the proportion of patients with potentially clinically significant (PCS) findings will be summarized by treatment group. Vital signs and ECG findings of potentially clinical significance are defined by post-baseline assessments or whether changes from baseline meet prespecified thresholds. The criteria for PCS will be detailed in the SAP.

For NCI-PRO-CTCAE, scores for each attribute (frequency, severity and/or interference) will be presented descriptively.

7.4.8 PK analysis

PK data analysis will be based on PKS. Plasma concentrations at each time point will be summarized descriptively using the scheduled sampling time points. The impact of food condition on safety will be explored if data allowed.

If needed, population pharmacokinetic analysis and exposure-response analysis will be performed based on the pooled dataset with other clinical trial data. These analysis results will be presented in a separate report.

8 Adverse Event Reporting

8.1 Definition

8.1.1 Definition and Classification of Adverse Events

8.1.1.1 Adverse Events (AEs)

An adverse event is any untoward medical occurrence, regardless of causal relationship to the investigational drug, that occurs in a patient from the time of signing the informed consent form until 30 days (including Day 30) after the last dose of study drug. Adverse events include the following:

- 1) Worsening of the original (before entering the clinical trial) medical conditions/diseases

(including aggravation of symptoms, signs, laboratory abnormalities);

2) Any new adverse medical condition (including symptoms, signs, newly diagnosed diseases);

3) Abnormal laboratory test results (e.g. blood chemistry, urinalysis) or other safety assessments (e.g. radiological examination, ECG, vital sign measurements), including those that worsen from baseline, considered clinically significant in the medical and scientific judgment of the Investigator. Not every abnormal laboratory test result qualifies as an adverse event. However, laboratory test result must be reported as an adverse event if it meets any of the following criteria:

- Is associated with accompanying symptoms.
- Requires clinical intervention, further investigation, or additional diagnostic testing.
- Leads to a change in study dosing or discontinuation from the study intervention.

If a clinically significant laboratory abnormality is not a sign of a disease or syndrome, the abnormality itself should be recorded as Adverse Event. If the laboratory abnormality can be characterized by a precise clinical term per standard definitions, the clinical term should be recorded as the adverse event.

8.1.1.2 Serious Adverse Events (SAEs)

An SAE is any adverse event, regardless of causality, occurring at any dose that:

- Results in death (excluding death that occurred after the Day 30 follow-up visit after the last dose, or due to confirmed disease progression/health status, instead of the study drug).
- Is life-threatening. Life-threatening refers to an event in which the patient is at risk of death at the time of the event. It does not refer to an event that hypothetically might have caused death if it were more severe.
- Requires hospitalization or prolongation of existing hospitalization. A planned hospitalization and/or surgical procedure prior to the patient's entry into the study will not be considered an adverse event provided there is no unexpected worsening during the study (e.g., surgery performed earlier than scheduled). Social and/or convenience admission to a hospital without untoward medical occurrence will not be considered an adverse event.
- Results in persistent or significant disability/incapacity.
- Is a congenital anomaly/birth defect.
- Is medically important. Medically important events are those that may not result in death or be life-threatening or require hospitalization, but may jeopardize the patient or may require intervention to prevent any of the outcomes listed in the definition of an SAE based on appropriate medical judgment and are also considered SAEs. Examples of such medical events include allergic bronchospasm requiring intensive

treatment in an emergency room or at home, blood cachexia or convulsions that do not require hospitalization, or development of drug dependence or drug abuse.

8.1.1.3 Suspected Unexpected Serious Adverse Reactions (SUSARs)

Suspected unexpected serious adverse reaction (SUSAR) refers to a suspected and unexpected serious adverse reaction in which the nature and severity of the clinical manifestation exceeds the available information such as the Investigator's Brochure of the investigational drug, the package insert of a marketed drug, or a summary of product characteristics.

8.1.2 Causality Definition

The investigator is obligated to assess the causality between study intervention and each AE/SAE.

The Investigator will determine the relationship to study drug administration according to the following criteria:

Related: there is a reasonable possibility of causal relationship between the study drug and the AE.

Unrelated: there is no reasonable possibility of causal relationship between the study drug and the AE.

“Reasonable possibility of causal relationship” means there are evidence to suggest a causal relationship.

The investigator will consider and investigate alternative causes, temporal association and use clinical judgment to determine the causal relationship.

The investigator should always make a causality assessment for every event before transmission of the SAE data to the sponsor, even if the investigator has minimal information to provide in the initial report.

The investigator may change causality opinion after follow-up information is received and send updated causality assessment in the SAE follow-up report.

8.1.3 Severity Criteria

The adverse events will be assessed for severity according to NCI CTCAE Version 5.0. For AEs not listed in CTCAE v5.0, assess the severity according to below criteria:

Grade	Clinical Description of Severity
Grade 1	Mild; asymptomatic or mild symptoms; clinical or diagnostic observations only; intervention not indicated.
Grade 2	Moderate; minimal, local or noninvasive intervention indicated; limiting age-appropriate instrumental Activities of Daily Living (ADL)*.

Grade	Clinical Description of Severity
Grade 3	Severe or medically significant but not immediately life-threatening; hospitalization or prolongation of hospitalization indicated; disabling; limiting self-care ADL **.
Grade 4	Life-threatening consequences; urgent intervention indicated.
Grade 5	Death related to AE.

**Instrumental ADL refer to preparing meals, shopping for groceries or clothes, using the telephone, managing money, etc.*

***Self care ADL refer to bathing, dressing and undressing, feeding self, using the toilet, taking medications, and not bedridden.*

8.1.4 Safety Reporting Period

The AE reporting period begins from the time that the patient provides signed informed consent, (i.e., prior to undergoing any study-related procedure/or receiving study drug), throughout the study and until 30 days (inclusive) after the last administration of study drug. Any serious adverse events that occur after the reporting period must also be reported immediately if a causal relationship with the study drug is suspected.

If a patient starts a new anti-tumor therapy, the safety report should end at the start of the new treatment.

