must be performed within 14 days prior to randomization. If the screening examination overlaps with the one conducted on C1D1 visit and the visit interval does not exceed 3 days, it is not necessary to repeat the examination on C1D1. For patients with screening failure, if the Investigator assesses that the original factors leading to screening failure have been excluded, the informed consent can be re-signed for re-screening.

2. All patients who complete Cycle 7 Visit (including MRI) and meet eligibility criteria will be eligible to enter Part 2 and receive treatment with open-label ABSK021, or end treatment. For patients who end treatment, an end-of-treatment (EOT) visit and a safety follow-up visit will be performed.
3. The End of Treatment Visit (EOT Visit) is required to be performed within 7 days after the patient permanently terminates the study drug treatment (if any test in EOT visit has been performed in the previous visit and the interval between two visits does not exceed 7 days, no need to repeat the tests in the EOT Visit). Patients who complete Part 1 and enter Part 2 do not need to have an EOT visit in Part 1.
4. Safety Follow-up Visit will occur 30 days \pm 7 days after the end of treatment (i.e., after the last dose of study drug) and patients will be contacted to collect new information (telephone follow-up, etc.) on adverse events and concomitant medications. Patients who complete Part 1 and enter Part 2 do not need to have a safety follow-up visit in Part 1.
5. Patients who discontinue treatment prematurely for reasons other than disease progression will be followed up for disease progression until disease progression, death, lost to follow-up, or the patient receives alternative anti-tumor therapy (including surgery), whichever occurs first. Disease progression follow-up will be conducted every 12 weeks (\pm 7 days). In principle, the maximum follow-up time will not exceed 12 months.
6. Demographic information (including sex, year of birth, age, ethnicity, race, etc.), prior medical history, current medical history, and detailed tumor history, including prior anti-tumor therapy information, will be collected at screening.

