4.3 Withdrawal and Replacement of Patients

4.3.1 Patient Withdrawal from the Study

Patients may withdraw voluntarily from the study at any time. The Investigator may also request the patient to withdraw from the study based on the actual clinical situation of the patient. Reasons for discontinuation of treatment or withdrawal from study may include:

- Withdrawal by subject;
- Adverse event;
- Lost to follow-up;
- Non-compliance with drug therapy;
- Physician decision;
- Pregnancy;
- Death;
- Progression disease;
- Study terminated by sponsor;
- The Investigator considered that withdrawal from the study may bring greater benefit to the patient.

If a patient voluntarily withdraws from the study, an attempt should be made to contact the patient to determine the reason for withdrawal. When a patient is early withdrawn from the study, all study procedures and assessments required for the EOT Visit should be completed, regardless of the withdrawal reason.

For patients who develop radiographic disease progression in Part 1 (assessed by **BOTH** BIRC and the investigator based on RECIST v1.1, respectively), if the investigator, after full assessments, deems that the benefit of early entry into Part 2 to receive open-label ABSK021 treatment outweighs the risk, with the approval of the sponsor, patients may enter Part 2 in advance under blinded conditions. However, it is strongly recommended that patients complete all visits in Part 1 according to the protocol (including visits after disease progression) before

entering Part 2.

For patients who develop radiographic disease progression (assessed by BIRC **OR** the investigator based on RECIST v1.1) in Part 2 or Part 3, if the investigator deems that continued treatment may bring benefit to the patient based on the benefit-risk maximization principle, after communication and agreement with the sponsor, the patient can continue to receive the treatment with the consent of the him/her.

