6.3.6 Progressive Disease Follow-up

Patients who discontinue treatment prematurely for reasons other than disease progression will be followed for disease progression until disease progression, death, loss to follow-up, or the patient receives alternative anti-tumor therapy (including surgery), whichever occurs first. Disease progression follow-up will be conducted every 12 weeks (± 7 days). In principle, the maximum follow-up time will not exceed 12 months.

For patients who withdraw from the study after prematurely treatment discontinuation and plan to undergo surgery, it is recommended to perform the surgery at least 3 weeks after the last dose (for patients in Part 1, the Investigator and the sponsor will jointly decide whether emergency unblinding is needed). Details of the surgery will be collected, including but not limited to, the reason for surgery, date, surgery name, copies of the surgical report and pathological reports (if any), ROM and PRO assessments (if any). Surgically resected tumor samples will be collected to assess the effect of this study drug on tumor cells, and disease recurrence will also be followed up by telephone (every 3 months) for a maximum follow-up period up to 12 months after the surgery (not applicable for placebo-treated patients).

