6.4.11 Adverse Events (AEs)

Adverse events (AEs) will be collected from the time the patient signs the informed consent form until 30 days (including Day 30) after the last dose of study drug. Please refer to Section 8 for the definition and reporting of adverse events.

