4.2. Data Handling Conventions and Definitions

4.2.1. Premature Withdrawal and Missing data

All available data from patients who were withdrawn from the study will be listed, and all available planned data will be included in summary tables and figures unless otherwise specified. Data from patients who withdraw after meeting the entry criteria but not treated will be only listed. Any data collected in the clinical database after a patient withdraws informed consent from all further participation in the trial should be removed from the database and not be included in the analysis data sets.

In general, missing data will not be imputed and only observed values will be analyzed unless otherwise specified. Any patient excluded from the summaries and/or statistical analyses will be documented along with the reason for exclusion in the clinical study report.

Partial missing dates for AE and concomitant medication will be imputed based on [Appendix 1](#) of Section 11.1. Partial dates will be displayed as captured in patient listing displays.

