7.2.2. Classifications of AEs

Treatment-emergent adverse event (TEAE) is defined as any AE that occurs after administration of the first dose of study drug and through 30 days (inclusive) after the last dose of study drug, any event that is present at baseline but worsens in severity or is considered treatment-related by the Investigator after administration of the first dose of study drug. AEs with start/end dates that are partially/completely missing will be imputed according to the specifications in [Appendix 1](#) to classify TEAEs.

Any TEAE will be defined as drug-related for related relationship to study drug judged by the investigator. Every attempt will be made to obtain complete information for AEs regarding severity (i.e., CTCAE Grade) and relationship to drug; however, in the rare case of missing data, missing AE relationship will be classified as “Related” in summary tables. The non-imputed raw data will be presented in AE listings.

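### Protocol 8.1.4 ends safety reporting when a new anti-tumor therapy starts, but AE collection elsewhere and every SAP safety window run to Day 30; the one scheduled safety contact may also fall before Day 30

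*Protocol*

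**What the plan says.** **Collection to Day 30, no exception.** Protocol 6.4.11 collects AEs from consent "until 30 days (including Day 30) after the last dose of study drug". Protocol 8.1.1.1 and the AE footnotes to the schedules (Table 1 footnote 19; Tables 2 and 3 footnote 17) give the same window.

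**Earlier stop.** Protocol 8.1.4 first runs the reporting period "throughout the study and until 30 days (inclusive) after the last administration of study drug". It then requires later SAEs to be reported if a causal link to study drug is suspected, and closes with: "If a patient starts a new anti-tumor therapy, the safety report should end at the start of the new treatment".

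**Surgery.** The estimand table and the progression follow-up rules count surgery as an alternative anti-tumor therapy. For patients who stop early and plan surgery, Protocol 6.3.6 says "it is recommended to perform the surgery at least 3 weeks after the last dose".

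**Contact.** Footnote 4 of Table 1 states "Safety Follow-up Visit will occur 30 days", with a tolerance of ±7 days, after the end of treatment. Tables 2 and 3 give the same timing. No other post-treatment safety contact is scheduled for every patient who stops.

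**Analysis.** SAP 7.2.2 counts TEAEs "through 30 days (inclusive) after the last dose of study drug". SAP 7.1 sets the on-treatment window at last dose + 30 days. SAP 7.2.4 ends EAIR time at risk, for an event-free patient who has stopped, at the earliest of last exposure + 30 days, death and data cutoff. None of these refers to a new therapy.

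**The concern.** The documents give two end dates for AE collection in the same patient. Take surgery on Day 21 after the last dose and, on Day 25, a non-serious AE or an SAE judged unrelated. Protocol 6.4.11 and 8.1.1.1 make it collectable; 8.1.4 does not. Sites may resolve this differently, so the safety database could depend on which section a site follows.

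The SAP carries the longer window throughout. Where a site follows 8.1.4, EAIR adds days on which AEs need not be collected to the denominator and no events to the numerator, so the rate is biased downward.

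The contact window is a second, separate gap. A call on Day 23 complies with the protocol, yet precedes the end of the period about which the patient should be asked. Comparing safety between arms is a stated secondary objective, so ascertainment should follow one rule.

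**Working it through.** The plan gives no figure here to reproduce. The check sets the rules side by side and then applies date arithmetic to the SAP's EAIR definition.

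**1. Which events are affected when a new therapy starts before Day 30**

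| Event after the new therapy, by Day 30 | 6.4.11 / 8.1.1.1 / schedule | 8.1.4 |
|---|---|---|
| Non-serious AE | collect | not required |
| SAE judged unrelated | collect | not required |
| SAE suspected related | collect | still reportable as a late SAE |

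The conflict is confined to the first two rows.

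**2. Days at stake**

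- Earliest contact: 30 − 7 = Day 23, leaving 30 − 23 = 7 of 30 days (23%) without a scheduled enquiry. Latest contact: 30 + 7 = Day 37, which covers the whole window.
- Surgery at 3 weeks: Day 21, so 30 − 21 = 9 of 30 days (30%) are cut.
- Outer limit: truncation on the day of the last dose, 30 of 30 days.

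**3. EAIR person-time for one event-free patient who stops**

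Planned time = days dosed + 30. Observed time = days dosed + day of truncation. Overstatement = planned / observed − 1.

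| Days dosed | Planned | Truncated Day 23 | Truncated Day 21 | Truncated Day 0 |
|---|---|---|---|---|
| 168 | 198 | 191 (3.7%) | 189 (4.8%) | 168 (17.9%) |
| 84 | 114 | 107 (6.5%) | 105 (8.6%) | 84 (35.7%) |
| 28 | 58 | 51 (13.7%) | 49 (18.4%) | 28 (107.1%) |

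The 168 days are the planned 24 weeks of Part 1; 84 and 28 are illustrative. The Day 23 column is an upper bound, because it supposes that nothing is learned after the call.

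**4. EAIR person-time for the 60-patient ABSK021 arm**

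Assume that a share q stop in Part 1 after E days of dosing, that the rest contribute 168 days each, that nobody has the event, and that every stopper loses L days.

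- Planned = 60 × [(1 − q) × 168 + q × (E + 30)]
- Observed = planned − 60 × q × L

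With q = 0.15 and E = 84: planned = 60 × (142.8 + 17.1) = 9,594 days.

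- L = 7: observed 9,594 − 63 = 9,531; overstatement 0.66%.
- L = 9: observed 9,594 − 81 = 9,513; overstatement 0.85%.
- L = 30: observed 9,594 − 270 = 9,324; overstatement 2.90%.

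Varying E over 28, 84 and 168 days:

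| q | L = 7 | L = 9 | L = 30 |
|---|---|---|---|
| 5% | about 0.2% | about 0.3% | about 0.9% |
| 15% | 0.6-0.7% | 0.8-0.9% | 2.7-3.1% |
| 30% | 1.2-1.6% | 1.6-2.0% | 5.4-7.1% |

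The 15% is the dropout allowance in Protocol 7.1, used only for scale; 5% and 30% are assumptions. Events missing from the numerator would lower the rate further, but the documents give nothing from which to size that.

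**The case against.** **A general rule with a specific exception.** Protocol 6.4.11 sends the reader to Section 8, and 8.1.4 is the Section 8 text on the reporting period. Ending collection at a new therapy is also a defensible choice. This is fair, but it does not dispose of the point: 8.1.1.1, also in Section 8, states the window without exception, and the SAP windows do not follow the exception.

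**Little drug remains.** With the half-life of 43.6 to 63.5 hours in Protocol 1.2.3, Day 21 is 7.9 to 11.6 half-lives after the last dose, so about 0.03% to 0.4% remains. This limits the clinical weight of the surgery case, though not the inconsistency.

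**Stronger readings that the documents do not support:**

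- *Suspected reactions are lost.* Protocol 8.1.4 keeps late SAEs reportable when a causal link is suspected, and 8.2.3 does the same for later deaths considered related.
- *A Day 23 call closes the window.* The ±7 days is a visit tolerance, and no text ends AE collection at the call. Spontaneous reports must be recorded (8.2.1), and weekly follow-up is recommended after discontinuation for an AE (5.5.2). What remains is the absence of a guaranteed enquiry covering the last days.
- *Consent withdrawal cuts the window too.* SAP 4.2.1 says "Any data collected in the clinical database after a patient withdraws informed consent from all further participation in the trial should be removed", while Protocol 4.3.1 asks that "all study procedures and assessments required for the EOT Visit should be completed, regardless of the withdrawal reason". These do not clearly conflict: the SAP rule covers only data collected after withdrawal from all participation, and a patient who agrees to EOT procedures has not gone that far.
- *Crude TEAE percentages assume the full window.* They use patient counts and have no time term. They can under-count events, but only EAIR carries the 30 days explicitly.
- *All planned dropouts are affected, and unevenly by arm.* The dropout allowance is not a count of patients starting a new therapy within 30 days, and the documents give no figure by arm. Patients who roll into Part 2 continue on study drug and need no Part 1 safety visit.

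**Conclusion.** The point stands as a matter of internal consistency. The new-therapy stop in Protocol 8.1.4 conflicts with the unconditional Day 30 rule elsewhere and is not mirrored in the SAP's TEAE, on-treatment or EAIR definitions. Non-serious AEs and SAEs judged unrelated can go unrecorded, and EAIR is biased slightly downward. The contact window is a lesser, separate weakness: up to 7 days may have no scheduled enquiry although collection formally continues.

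At arm level the person-time effect is under 1% for 7 or 9 days lost, and about 3% if all 30 are, when 15% stop in Part 1. It is larger for an individual who stops early. These figures suppose that every stopper is truncated, which overstates the likely effect. They also rest on surgery counting as a new therapy under 8.1.4, as it does elsewhere in the plan. The primary efficacy analysis is untouched.

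**What to change.** 1. **One end-of-collection rule.** Reconcile Protocol 8.1.4 with 6.4.11, 8.1.1.1, 8.1.1.2, 8.2.3 and the schedule footnotes, and say whether surgery counts as a new therapy. Section 8.1.1.2 needs attention because it excludes deaths after the Day 30 follow-up visit, and that visit may occur on Day 23, whereas 8.2.3 requires all deaths in the reporting period to be reported.
2. **Match the analysis.** End the TEAE and on-treatment windows (SAP 7.1 and 7.2.2; Protocol 7.4.7 and 7.4.7.1) and the EAIR time at risk (SAP 7.2.4) on that date. If collection stops at a new therapy, add its start date to the list of earliest dates in EAIR. The schedules already record new anti-tumor therapy at the safety and progression follow-ups. If collection runs to Day 30 regardless, remove the stop from 8.1.4 and flag events that follow the new therapy.
3. **Contact window.** Set the safety contact so that it cannot precede the end of collection.

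The cost is wording in both documents and some calls a few days later. If the full window is kept, a few more events confounded by the new therapy will also be recorded.
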